## **Background**

A. Significance A.1. Metabolically Healthy Obesity and Obesity with the Metabolic Syndrome (MetS) Obesity affects 38% of the U.S. population (5) and is related to many serious medical comorbidities, including type 2 diabetes, heart disease, some cancers, osteoarthritis, and obstructive sleep apnea (6,7). However, approximately 10-30% of persons with obesity remain metabolically healthy (8), characterized by decreased visceral and liver fat, C-reactive protein (CRP), and mean adipocyte size, and increased serum adiponectin and adipocyte insulin sensitivity (9). The other 70-90% of obese individuals have MetS, a cluster of conditions-increased blood pressure, high blood sugar, excess abdominal body fat, and abnormal cholesterol or triglyceride levels-occurring together that increase the risk of cardiovascular disease and diabetes (8). Behavioral weight loss approaches are effective at helping persons reduce weight by 5-10% of their initial body weight (7), but obesity prevention remains a primary public health goal, along with identifying behavioral strategies to optimize weight loss and maintenance. Of the many factors contributing to the obesity epidemic, the timing of food consumption is recognized as a significant contributor to body weight regulation (1-4,10). A.2. Circadian Regulation of Feeding and Metabolism The underlying mechanisms governing the circadian rhythms of fundamental processes such as sleeping and eating, are well characterized. The circadian system enables organisms to synchronize behaviors, metabolism, and physiological processes to sleep-wake cycles (11,12). The core clock mechanism is based on a feedback loop involving the transcription factors BMAL1, CLOCK, and NPAS and their targets (11). Circadian rhythms are ordered hierarchically in mammals with the hypothalamic suprachiasmatic nucleus (SCN) controlling a network of central and peripheral clocks. The SCN responds primarily to light and synchronizes behavioral and physiological rhythms via circadian oscillations in extra-SCN brain circuits and peripheral tissues (11). When food is abundant and animals are kept under normal light-dark (LD) cycles, photoperiod is the primary zeitgeber (time-giver) for the master clock in the SCN, and produces a near-24 rhythm in feeding behavior and metabolism (11). Macronutrients (i.e., glucose, fatty acids, and amino acids) and nutrient-sensing molecules (e.g., AMPK, SIRT1, mTOR, and CRTC2) entrain central and peripheral clocks, changing the timing and amplitude of gene expression rhythms and metabolic pathways (11). However, a disruption in the timing of food availability induces another regulator-the food entrainable oscillator (13-15). Unlike the SCN, peripheral clocks in the liver, other organs, and the gut microbiome respond to the timing of feeding (12). Rodent studies have demonstrated that eating out of phase

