
metabolic changes associated with the daytime and delayed eating conditions. We hypothesize clock genes and adipocyte genes will change in the daytime vs. delayed conditions, allowing discrimination of the 2 states. These altered genes may serve as therapeutic, pharmacological targets (82) and biomarkers for obesity-related complications. We will also correlate AT gene expression with fasting lipid and glucose levels. In addition, as AT and blood will be collected on the same day, we will compare pre-post changes in AT and blood expression using meta-analyses, to identify how different tissues relate to each other as a function of eating condition, and to identify tissue-specific changes resulting from a daytime vs. delayed eating schedule. Such knowledge would also be advantageous for collection methods, given the limited accessibility and subject burden involved in AT biopsies vs. the minimally invasive, accessible collection of blood. Finally, genes that emerge across AT and blood would be viable biomarkers and targets for future studies. A.4b. Blood Transcriptome: Links to Obesity, Circadian Rhythms and Timed/Delayed Eating in Humans. Blood Transcriptome and Obesity. Blood gene expression profiling in obese persons has identified distinct biological pathways associated with obesity (83-85) and BMI (86). In addition, dietary patterns, dietary challenges and high fat diets all alter blood gene expression (87-89). Blood Transcriptome and Circadian Rhythms. Transcriptomic studies using peripheral blood have shown that gene expression and rhythmicity are affected by desynchrony between sleep and circadian phase (i.e., mistimed sleep), constant routines, and sleep loss, whereby the number and/or amplitude of genes exhibiting circadian rhythmicity is altered (59,90-98). These studies highlight the gene expression interrelationships between circadian rhythmicity and sleep homeostasis in blood. We propose to extend the analysis of blood transcriptome in circadian rhythm studies to obesity and timed eating paradigms. Timed/Delayed Eating and Blood Gene Expression. Since timed/delayed eating impacts circadian rhythms (sections A.3b. and A.3c.), and blood shows circadian rhythms in gene expression, the timing of eating should affect blood gene expression. Notably, how delayed timed eating affects blood gene expression in humans remains unknown. As such, we will compare the daytime vs. delayed eating schedule on the phase and cycling amplitude of gene expression profiles from blood. We hypothesize central and peripheral clock genes will show significant changes in the daytime vs. delayed conditions, allowing discrimination of the 2 states. In addition, we will cluster genes by phase for each 4h sample bin and compare these clusters with circadian rhythm hormone phase profiles using correlational analysis to identify how different blood markers relate to each other as a function of eating condition; this may allow for identification of additional genes implicated in timed eating. A.5. Study Team Experience. The proposed research will be conducted by investigators from UPenns Center for Weight and Eating Disorders (CWED), Division of Sleep and Chronobiology, Division of Endocrinology, Diabetes, and Metabolism, and Department of Neuroscience and CHOPs Department of Biomedical and Health Informatics all within close proximity (10 min walk). MPIs [name] and [name] have collaborated on prior research efforts and have established a strong working relationship. They have a R21 grant together and have published on the circadian and metabolic characteristics of NES (43) and a review on delayed eating (2). MPI [name] has collaborated with Co-I [name] on several projects including recent investigations on the human and rat microbiome (99) and metabolome (100). MPI [name] has also collaborated with Co-I [name] on a recent investigation of changes in human and rat microRNAs during sleep loss (101). MPI [name] has worked with Co-I [name] on her current R21, as he served as the physician contact for the inpatient assessments; Co-I [name] has also worked with our group at CWED on a study using FSIGT in bariatric and behavioral weight loss patients (102). The investigators have extensive research experience in eating behaviors, weight management, and obesity in humans ([name]); circadian rhythms, sleep-wake and energy balance in humans ([name]); molecular and cellular mechanisms of circadian rhythms ([name]); endocrinology and metabolism in humans ([name]); and biomedical and health bioinformatics ([name]). Our R21 study; human studies of NES and metabolic changes with sleep loss, weight loss, and metabolic disorders (30,40,41,103-108); long-term, experimental measurement of human circadian rhythms, sleep, metabolism and activity (109-120); studies on insulin sensitivity, free fatty acid dynamics and AT (121-123); and studies on transcriptomics (124-126), bring a unique set of skills to examine this translational topicthe impact of the timing of eating on body mass and fat, energy metabolism and hormonal regulation, and its circadian mechanisms in persons with obesity. A.6. Scientific and Public Health Relevance of the Proposed Project. The timing of eating impacts weight and metabolic functioning, but most studies have been in rodents or normal weight persons. The proposed study extends this work to metabolically healthy persons with obesity, but who remain at risk of developing MetS and diabetes. This translational human experiment controlling for eating and sleep timing, caloric intake, and exercise will uncover numerous potential circadian mechanisms resulting from the metabolic- and weight-related impact of a daytime vs. delayed eating schedule that contribute to the pathophysiology of obesity. Determining such circadian-dependent mechanisms using deep phenotyping will identify targets for medical interventions for obesity and for prevention of the MetS

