
amplitude and phase of expression data will use linear mixed effects cosinor analysis (154), which accounts for systematic inter-individual differences. We will fit separate linear mixed effect models for ghrelin and leptin phases as described above. For transcriptomics, gene expression count data will be normalized in R using the TMM function in edgeR (155) and voom in the limma package (156). We will use linear mixed effect models against RNA-seq depth count data to test the differences in genes between the daytime and delayed conditions. Mixed model analysis will be done on the normalized RNA count data to adjust for effects such as condition order and random subject effects using the lme4 package (157) in the R statistical environment version R-3.2.3. P-values for each test will be generated from the lmer results using the Anova function in the R car package (158). Coefficients of the lme analyses will represent the log2 fold change between the two conditions tested (change in daytime vs. change in delayed). We will use a p-value cutoff adjusted by false discovery rate of 0.05 to detect all RNA changes of statistical significance comprehensively. Pathway analysis will be run in various functional enrichment analysis tools, e.g., Metacore (Thomson Reuters) and Ingenuity Pathway Analysis software (Qiagen). We also will cluster genes by phase for each of the 4h sample bins and compare them with circadian rhythm hormone phase profiles using correlational analysis to identify how different blood markers are related as a function of eating condition; this may allow for identification of additional genes implicated in timed eating. Each phase cluster can also be analyzed for statistical significance of enrichment against a number of biological pathways and gene sets. Specific Aim 3. The goal of this aim is to compare the daytime vs. delayed eating schedule on insulin sensitivity and free fatty acid dynamics and on AT gene expression. Changes in insulin sensitivity and free fatty acid dynamics by condition will be compared with linear mixed-effects models. Statistical analysis of gene expression data will be conducted as described for Specific Aim 2. As AT and blood will be collected on the same day, we will also compare pre-post changes in AT and blood expression using meta-analyses, to identify how different tissues relate to each other as a function of eating condition. This will also allow indirect comparison of hormonal data with AT gene expression. Finally, we will correlate AT gene expression with fasting lipid and glucose levels.

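### The hypothesised clock and adipocyte genes have no pre-listed test family; the only stated expression rule is a transcriptome-wide FDR, which costs much power when effects are moderate and few other genes move

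*Combined protocol and SAP*

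**What the plan says.** Two hypotheses about named classes of genes stand in the Background section. For blood (A.4b): "We hypothesize central and peripheral clock genes will show significant changes in the daytime vs. delayed conditions". For adipose tissue (A.4a): "We hypothesize clock genes and adipocyte genes will change in the daytime vs. delayed conditions". Section A.2 gives a starting point for a clock-gene list: "The core clock mechanism is based on a feedback loop involving the transcription factors BMAL1, CLOCK, and NPAS and their targets".

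The Analysis Plan, Specific Aim 2, fits gene-wise mixed models whose coefficients are log2 fold changes between conditions. It then states the decision rule: "We will use a p-value cutoff adjusted by false discovery rate of 0.05 to detect all RNA changes of statistical significance comprehensively". Specific Aim 3 carries the same approach to adipose tissue: "Statistical analysis of gene expression data will be conducted as described for Specific Aim 2".

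Three further expression analyses are planned:
- Rhythm: "amplitude and phase of expression data will use linear mixed effects cosinor analysis".
- Gene sets: "Pathway analysis will be run in various functional enrichment analysis tools", with no set named.
- Phase clusters: enrichment against pathways and gene sets, worded as optional.

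Neither clock genes nor adipocyte genes are mentioned anywhere in the Analysis Plan. The Accrual section gives no effect size for expression. It argues that power is sufficient from the sample sizes of other within-subject studies.

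**The concern.** A hypothesis about a short set of genes that could be written down in advance is given the same threshold as every other transcript. Under an FDR procedure, that threshold depends on how many genes are tested and how many of them show small p-values. Whether a truly changed clock gene is declared significant can then depend on how many unrelated genes also move.

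Without a list, there are two ways to judge the hypothesis. One is the transcriptome-wide cut-off, which may be far too strict for it. The other is a list assembled after the results are known, which would carry little weight. Transcriptomics is a secondary outcome, but these genes are the circadian mechanism the study sets out to examine.

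**Working it through.** **Inputs from the documents.** 40 enrolled; 90% retention; two-sided paired t-test; alpha 0.05 (Objectives and Accrual). FDR 0.05 for expression (Analysis Plan).

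**Assumed, because the documents do not say.** 15,000 genes tested; genes independent; one paired contrast per gene; a list of 15 genes of which 8 truly change; standardised paired effect d from 0.5 to 1.0; 0, 100, 1,000 or 3,000 other genes moving by the same d.

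**Step 1: the plan's own figure.** 40 × 0.90 = 36, as stated. By the noncentral t distribution, n=36 at two-sided alpha 0.05 gives 80% power at d=0.48. Effects of about 0.5 are therefore the size this sample can detect in a single unadjusted test.

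**Step 2: why the family matters.** Benjamini-Hochberg compares the k-th smallest of m p-values with 0.05 × k/m.
- Whole transcriptome, first step: 0.05/15,000 = 0.0000033. Power for one gene is 1.9% at d=0.5, 5.8% at d=0.6 and 67% at d=1.0; 80% power needs d=1.08.
- List of 15, first step: 0.05/15 = 0.0033. Power is 45% at d=0.5 and 67% at d=0.6; 80% power needs d=0.67.
- List of 15, eighth step: 0.05 × 8/15 = 0.027. Power is 75% at d=0.5 and 90% at d=0.6.

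**Step 3: simulation.** Noncentral-t statistics (n=36), with Benjamini-Hochberg applied to all 15,000 genes and, separately, to the 15 listed. Share of the 8 true changes found:

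| d | 0 others move | 100 | 1,000 | 3,000 | Pre-listed family |
|---|---|---|---|---|---|
| 0.5 | 3% | 6% | 31% | 52% | about 70% |
| 0.6 | 8% | 27% | 60% | 77% | about 89% |
| 0.8 | 40% | 78% | 93% | 98% | about 99% |
| 1.0 | 83% | 97% | 100% | 100% | about 100% |

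Monte Carlo error is a few percentage points at most. The realised FDR inside the list is 1-3%, in line with the expected 0.05 × 7/15 = 2.3% (7 of the 15 listed genes unchanged).

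**Step 4: sensitivity, no other gene moving.**
- All listed genes changed, 12,000 to 20,000 genes tested, lists of 10 to 20: the transcriptome-wide rule finds 1-2% at d=0.48, 7-10% at d=0.6, 44-56% at d=0.8 and 85-90% at d=1.0.
- Only 5 of 15 listed genes changed, 15,000 tested: transcriptome-wide against listed is 2% against 59% at d=0.48, 7% against 84% at d=0.6, 34% against 98% at d=0.8 and 81% against 100% at d=1.0.

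**The case against.** The strongest reply is that the worst case fits the documents poorly. The Background describes clock genes as regulators with many downstream targets, including some adipokines. If they shift, other genes should shift too, and the column with no other gene moving becomes the least likely. This stands as a limit on size. With 1,000 others moving at d=0.6 the transcriptome-wide rule finds 60%, and at d=1.0 it does well in every column. The gap at d=0.5 remains material even with 3,000 others moving: 52% against about 70%.

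Second, the simulated test is one paired difference per gene, whereas A.4b frames the blood comparison as phase and cycling amplitude, with seven samples per visit. Repeated sampling could raise the effective d in blood. Adipose tissue has one sample per visit and gains nothing from this. The point also shows that the parameter behind the blood hypothesis needs naming.

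Third, the cosinor and enrichment analyses mean the FDR rule is not the only look at expression, and the FDR sentence is not tied explicitly to the cosinor tests. That is so. But none of these analyses fixes a set of clock or adipocyte genes or a decision rule for them.

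Fourth, a reader might go on to attack the claim that the changes will allow the two states to be discriminated. On the same assumptions, with within-person correlation 0.3-0.8, one gene at d=0.6 gives an AUC of only 0.61-0.69. But the hypothesis concerns several genes, and eight such independent genes combined give 0.78-0.92. The argument does not hold and is not part of this point.

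**Conclusion.** The gap is real: genes hypothesised in advance have no list, no family and no decision rule of their own. The loss of power is large for moderate effects (d of about 0.5-0.6) when few other genes move: about 3-8% of true changes found with none moving, against 70-89% with a list. It is small for large effects or broad shifts in the transcriptome. All figures rest on assumed numbers of genes, independence between genes and assumed effect sizes.

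Stronger readings are tempting but not supported. A reader might infer that real clock-gene changes would usually be missed; without an expression effect size, the documents cannot show that. A reader might infer that clock genes are the study's single targeted expression hypothesis; adipocyte genes are hypothesised too and have the same gap. A reader might infer that the trial will report its hypothesis as unsupported if these genes miss the cut-off; no text says so. This is an inexpensive improvement to a secondary analysis and should be made.

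**What to change.** In Specific Aims 2 and 3, before the expression data are analysed:

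1. Fix a short list of clock genes for blood and adipose tissue, starting from the factors and targets in Background A.2, and a short list of adipocyte genes for adipose tissue.
2. Test the listed genes at FDR 0.05 within the list, separately by tissue.
3. Name the parameter tested: cosinor phase and amplitude in blood; the daytime-versus-delayed difference in change in level in adipose tissue. If both phase and amplitude are tested, count both in the blood family (15 genes would give 30 tests).
4. Keep the rest of the transcriptome as a discovery family at FDR 0.05.

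The cost is the lists and a few sentences of plan text, with no new participants, samples or assays. The downside is slightly more expected false discoveries in total, because FDR is controlled within several families instead of one.

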### **Study Design**

#### **Phase\***

Not applicable

#### **Design**

The study is a randomized within-subjects cross-over design.

#### **Study duration**

The total duration of subject participation will be approximately 19 wks: baseline assessments will take approximately 1 wk, the first eating condition will last 8 wk, followed by a 2-wk washout, and then followed by the second 8-wk eating condition (see Table 2 for study events for participants). The timeline of the proposed study will be 5 years to enroll and complete all subjects.

#### **Resources necessary for human research protection**

Describe research staff and justify that the staff are adequate in number and qualifications to conduct the research. Describe how you will ensure that all staff assisting with the research are adequately informed about the protocol and their research related duties. Please allow adequate time for the researchers to conduct and complete the research. Please confirm that there are adequate facilities for the research.

The proposed research will be conducted by investigators from UPenns Center for Weight and Eating Disorders (CWED), Division of Sleep and Chronobiology, Division of Endocrinology, Diabetes, and Metabolism, and Department of Neuroscience and CHOPs Department of Biomedical and Health Informaticsall within close proximity (10 min walk). MPIs [name] and [name] have collaborated on prior research efforts and have established a strong working relationship. They have a R21 grant together and have published on the circadian and metabolic characteristics of NES (43) and a review on delayed eating (2). MPI [name] has collaborated with Co-I [name] (at CHOP)on a recent investigation of changes in human and rat microRNAs during sleep loss (101). MPI [name] has worked with Co-I [name] on her current R21, as he served as the physician contact for the inpatient assessments; Co-I [name] has also worked with our group at CWED on a study using FSIGT in bariatric and behavioral weight loss patients (102). The investigators have extensive research experience in eating behaviors, weight management, and obesity in humans ([name]); circadian rhythms, sleep-wake and energy balance in humans ([name]); endocrinology and metabolism in humans ([name]); and biomedical and health bioinformatics ([name]). Our R21 study; human studies of NES and metabolic changes with sleep loss, weight loss, and metabolic disorders (30,40,41,103-108); long-term, experimental measurement of human circadian rhythms, sleep, metabolism and activity (109-120); studies on insulin sensitivity, free fatty acid dynamics and AT (121-123); and studies on transcriptomics (124-126), bring a unique set of skills to examine this translational topicthe impact of the timing of eating on body mass and fat, energy metabolism and hormonal regulation, and its circadian mechanisms in persons with obesity. In addition, all study staff will receive a copy of the protocol which will also be reviewed with them in detail to ensure they are adequately informed about the protocol and their individual duties.

## **Characteristics of the Study Population**

#### **Target population**

Obese men and women ages 21-50 years old with a BMI between 30-50kg/m^2 without metabolic syndrome.

#### **Subjects enrolled by Penn Researchers**

40

#### **Subjects enrolled by Collaborating Researchers**

0

## Accrual

Participants will be recruited through postings on campus and nearby workplaces, pamphlets to Penn Medicine practices, internet advertisements, and local media appearances. Participants will live/work within a 5 mi radius of the Hospital of the University of Pennsylvania for compliance with study visits and for ease of food delivery. UPenn currently employs 17,500 faculty and staff. Penn Medicine employs 21,626 people, and West Philadelphia (zip code 19104) has an adult population of about 54,718 (36% white, 40% black, 15% Asian; 50% female) (131). They will be required to have access to a personal electronic device for taking and sending photographs to study staff and receiving and responding to a link to REDCap (Research Electronic Data Capture) with daily queries regarding eating, sleep, and exercise parameters. We required this for our R21, and did not encounter issues; we expect this will not greatly impact recruitment. Power analysis for the outcome variables are based on our R21 data, which was designed to generate effect sizes (Cohens d; 127) for a R01 application; it uses the same study design sequence consisting of 2 orders (AB/BA design). Table 1 (see section C.1.) summarizes the power estimates, all assuming a 90% retention rate (n=36), a 2-sided paired t-test, and  $\alpha=0.05$  (G\*Power 3.1 program; 159). Power is above 80% for 7 of the 11 variables proposed, including weight, RQ, total cholesterol, triglycerides, insulin, trunk fat%/leg fat%, and circadian phase of leptin. Gene expression studies have not been done previously using our proposed design. However, within-subjects blood transcriptome studies in the circadian rhythm and obesity fields have detected gene expression changes using sample sizes of n=9-28 (84,90-92,94,95,98); similarly, within-subjects AT transcriptome studies in obese subjects have detected gene expression changes using sample sizes of n=6-20 (64,65,67,68). Thus, we anticipate having enough power to detect AT and blood expression changes (Specific Aims 2 and 3) between the daytime and delayed conditions using a within-subjects design and a sample size of n=36. Similarly, insulin sensitivity and free fatty acid dynamics studies have not been done previously using our proposed design. However, FSIGT studies have detected significant insulin sensitivity and free fatty acid dynamics changes using sample sizes of n=10-20 (121-123); thus, we anticipate having enough power to detect these changes (Specific Aim 3) between the daytime and delayed conditions using a within-subjects design and a sample size of n=36. Therefore, we will have sufficient power to detect significant differences between conditions in almost all of outcome variables for Specific Aims 1, 2 and 3, assuming a 10% study dropout rate (final sample size, n=36).
